10.1. Appendix 1: Regulatory, Ethical, and Study Oversight Considerations

10.1.1. Regulatory and Ethical Considerations

- This study will be conducted in accordance with the protocol and with the following:
 - Consensus ethical principles derived from international guidelines including the Declaration of Helsinki and Council for International Organizations of Medical Sciences (CIOMS) International Ethical Guidelines
 - Applicable ICH GCP Guidelines
 - Applicable laws and regulations
- The protocol, protocol amendments, ICF, Investigator Brochure, and other relevant documents (e.g., advertisements) must be submitted to an IRB/IEC by the investigator and reviewed and approved by the IRB/IEC before the study is initiated.
- Any amendments to the protocol will require IRB/IEC approval before implementation of changes made to the study design, except for changes necessary to eliminate an immediate hazard to study participants.
- The investigator will be responsible for the following:
 - Providing written summaries of the status of the study to the IRB/IEC annually or more frequently in accordance with the requirements, policies, and procedures established by the IRB/IEC
 - Notifying the IRB/IEC of SAEs or other significant safety findings as required by IRB/IEC procedures
 - Providing oversight of the conduct of the study at the site and adherence to requirements of 21 CFR, ICH guidelines, the IRB/IEC, European regulation 536/2014 for clinical studies (if applicable), and all other applicable local regulations
 - Reporting to the sponsor or designee significant issues related to participant safety, participant rights, or data integrity

After reading the protocol, each principal investigator will sign the protocol signature page and send a copy of the signed page to a Lilly representative.

The CSR coordinating investigator will sign the final CSR for this study, indicating agreement that, to the best of his or her knowledge, the report accurately describes the conduct and results of the study.

10.1.2. Informed Consent Process

- The investigator or his/her representative will explain the nature of the study, including the risks and benefits, to the participant or his/her legally authorized representative and answer all questions regarding the study.

- Participants must be informed that their participation is voluntary. Participants or their legally authorized representative will be required to sign a statement of informed consent that meets the requirements of 21 CFR 50, local regulations, ICH guidelines, Health Insurance Portability and Accountability Act (HIPAA) requirements, where applicable, and the IRB/IEC or study center.
- The medical record must include a statement that written informed consent was obtained before the participant was entered in the study and the date the written consent was obtained. The authorized person obtaining the informed consent must also sign the ICF.
- Participants must be re-consented to the most current version of the ICF(s) during their participation in the study.
- A copy of the ICF(s) must be provided to the participant or the participant's legally authorized representative and is kept on file.

Participants who are rescreened are required to sign a new ICF.

10.1.3. Data Protection

- Participants will be assigned a unique identifier by the sponsor to protect the participant's personal data. Any participant information, such as records, datasets or tissue samples that are transferred to the sponsor will contain the identifier only. Participant names or any information which would make the participant identifiable will not be transferred.
- The participant must be informed that the participant's personal study-related data will be used by the sponsor in accordance with local data protection law. The level of disclosure must also be explained to the participant who will be required to give consent for their data to be used as described in the informed consent. This is done by the site personnel through the informed consent process.
- The participant must be informed through the informed consent by the site personnel that their medical records may be examined by Clinical Quality Assurance auditors or other authorized personnel appointed by the sponsor, by appropriate IRB/IEC members, and by inspectors from regulatory authorities.
- The sponsor has processes in place to ensure information security, data integrity, and data protection. These processes address management of data transfer and prevention and management of unauthorized access, disclosure, dissemination, alteration, or loss of information or personal data. These processes include appropriate contingency plan(s) for appropriate and timely response in the event of a data security breach.
- The transfer of personal data is subject to appropriate safeguards through contractual agreements and processes. The sponsor's processes are compliant with local privacy laws and relevant legislations including the General Data Protection Regulation (GDPR).

10.1.4. Committees Structure

The primary endpoint TFFS will be assessed by BICR. The BICR will be composed of independent radiologists to perform response assessments and determination of disease progression per RECIST 1.1 and if needed, independent clinicians to review the case report forms (CRF) and determine whether discontinuation for unacceptable toxicity meets the criteria for a TFFS event as defined above

10.1.5. Dissemination of Clinical Study Data

Dissemination of study data will be performed according to all applicable Lilly and international policies.

Reports

The sponsor will disclose a summary of study information, including tabular study results, on publicly available websites where required by local law or regulation.

The summary of results will be posted within the time frame specified by local law or regulation. If the study remains ongoing in some countries and a statistical analysis of an incomplete dataset would result in analyses lacking scientific rigor (for example, underpowered) or compromise the integrity of the overall analyses (for example, trial not yet unblinded), the summary of results will be submitted within 1 year after the end of the study globally or as soon as available, whichever is earlier.

10.1.6. Data Quality Assurance

To ensure accurate, complete, and reliable data, the sponsor or its representatives will do the following:

- provide instructional material to the study sites, as appropriate
- provide sponsor start-up training to instruct the investigators and study coordinators. This training will give instruction on the protocol, the completion of the CRFs, and study procedures.
- make periodic visits to the study site
- be available for consultation and stay in contact with the study site personnel by mail, telephone, and/or fax
- review and verify data reported to detect potential errors

In addition, the sponsor or its representatives will periodically check a sample of the participant data recorded against source documents at the study site. The study may be audited by the sponsor or its representatives and/or regulatory agencies at any time. Investigators will be given notice before an audit occurs.

The investigator will keep records of all original source data. This might include laboratory tests, medical records, and clinical notes. If requested, the investigator will provide the sponsor, applicable regulatory agencies, and applicable ERBs with direct access to original source documents.

Data Capture System

The investigator is responsible for ensuring the accuracy, completeness, legibility, and timeliness of the data reported to the sponsor.

An electronic data capture system (EDC) will be used in this study for the collection of CRF data. The investigator maintains a separate source for the data entered by the investigator or designee into the sponsor-provided EDC system. The investigator is responsible for the identification of any data to be considered source and for the confirmation that data reported are accurate and complete by signing the CRF.

Additionally, electronic Clinical Outcome Assessment (eCOA) data questionnaires and scales will be directly recorded by the patient, into an instrument (e.g., an electronic device). The eCOA data will serve as the source documentation and the investigator does not maintain a separate, written or electronic record of these data.

Data collected via the sponsor-provided data capture system will be stored at third party. The investigator will have continuous access to the data during the study and until decommissioning of the data capture system. Prior to decommissioning, the investigator will receive an archival copy of pertinent data for retention.

Data managed by a central vendor, such as laboratory test data, will be stored electronically in the central vendor's database system and the results will be provided to the investigator for review and retention. Data will subsequently be transferred from the central vendor to the Lilly data warehouse.

Data from complaint forms submitted to Lilly will be encoded and stored in the global product complaint management system.

10.1.7. Source Documents

Source documents provide evidence for the existence of the participant and substantiate the integrity of the data collected. Source documents are filed at the investigator's site.

Data reported on the CRF or entered in the eCRF that are transcribed from source documents must be consistent with the source documents or the discrepancies must be explained. The investigator may need to request previous medical records or transfer records, depending on the study. Also, current medical records must be available.

10.1.8. Study and Site Closure

10.1.8.1. Discontinuation of the Study

The study will be discontinued if Lilly judges it necessary for medical, safety, regulatory, or other reasons consistent with applicable laws, regulations, and GCP.

10.1.8.2. Discontinuation of Study Sites

Study site participation may be discontinued if Lilly, the investigator, or the ERB of the study site judges it necessary for medical, safety, regulatory, or other reasons consistent with applicable laws, regulations, and GCP.

10.1.9. Provisions for Changes in Study Conduct During Emergencies

There may be times due to exceptional circumstances where it may not be feasible for patients to come to investigator sites for study-required visits. To mitigate the risk of patients missing visits, to allow patients to safely continue to receive care, and maintain the data integrity of the study, the following may be allowed on a case-by-case basis following approval from the sponsor and if permitted by local regulations.

- Remote/virtual visits and/or extended visit windows may be used. Medically qualified site personnel may collect study required information (e.g., AEs, concomitant medications, ECOG status, and study treatment compliance) via videoconference (preferred) or phone. Visit or cycle windows as defined in the schedule of activities may be extended to facilitate the ability to perform study-specific assessments at the site, which is preferred to remote/virtual visits. Every effort should be made to return to in-clinic visits as soon as reasonably possible and safe for the patient and investigator/site staff.
- Labs, ECGs and/or tumor imaging may be obtained at a local (non-study) site. Laboratory results (including reference ranges), ECGs and/or scans obtained at a local lab must be filed and reviewed by the study investigator or qualified designee in a timely manner.
- For patients that meet the protocol criteria to continue or restart dosing, local processes may be leveraged to deliver drug directly to patients.
- A remote informed consent process may be implemented.

Site personnel are responsible for documenting in the source records all changes in study conduct, relevant communications (patient and sponsor), and dispensing/shipment records of IP and indicating the actions taken as a result of exceptional circumstances mitigation. If mitigations are approved by the sponsor, additional instructions on the process and documentation will be provided to the site. Additional mitigations may be approved by the sponsor and will be tracked as protocol deviations as required.

10.2. Appendix 2: Clinical Laboratory Tests

The tests detailed below will be performed by the indicated laboratory.

- Local laboratory results are required only in the event that the central laboratory results are not available in time for inclusion/exclusion determination, study intervention administration, and/or response evaluation or for assessments that are performed remotely/virtually. If a local sample is required, it is important that the sample for central analysis is obtained at the same time (e.g., hepatic safety labs). Additionally, if the local laboratory results are used to make either a study intervention decision or response evaluation, this should be reported into the CRF as an AE. If there is an abnormal laboratory value or abnormal value for any other diagnostic or screening test (e.g., blood pressure increased, neutrophils decreased, etc.) and it is known to be related to a diagnosis (e.g., hypertension, neutropenia, etc.) this should be reported into the CRF as an AE. Do not enter the test abnormality, enter the disease diagnosis or categorical term.
- Additional tests may be performed at any time during the study as determined necessary by the investigator or required by local regulations, and clinically significant findings should be reported in the CRF as an AE.
- Enrollment and treatment decisions may be based upon local laboratory results. Discrepancies between local and central laboratory results will not be considered a protocol deviation.

Hematology – local laboratory

- | | | |
|----------------------------|----------------------|--------------------|
| • Leukocytes (WBC) | • Eosinophils | • Hematocrit (HCT) |
| • Neutrophils ^a | • Basophils | • Platelets (PLT) |
| • Lymphocytes | • Erythrocytes (RBC) | |
| • Monocytes | • Hemoglobin (HGB) | |

Coagulation – local laboratory

- Activated partial thromboplastin time (aPTT) or partial thromboplastin time (PTT)
- International normalized ratio (INR) or prothrombin time (PT)

Chemistry –central laboratory^{b,c}

Serum concentrations of:

- | | |
|------------------------------------|-------------------|
| • Alanine aminotransferase (ALT) | • Creatinine |
| • Albumin | • Glucose, random |
| • Alkaline phosphatase | • Magnesium |
| • Aspartate aminotransferase (AST) | • Phosphorus |
| • Bicarbonate | • Potassium |
| • Bilirubin, total | • Sodium |
| • BUN or blood urea | • Total protein |
| • Calcium | |
| • Chloride | |

Hepatic monitoring –central laboratory^{b,c}

- | | |
|------------------------------------|---------------------|
| • Alanine aminotransferase (ALT) | • Bilirubin, direct |
| • Aspartate aminotransferase (AST) | • Bilirubin, total |
| • Alkaline phosphatase | |

Thyroid panel – local laboratory

- Triiodothyronine (T3) (free or total, per local standard of care)
- Thyroxine (T4) (free or total, per local standard of care)
- Thyroid stimulating hormone (TSH)

Calcitonin, CEA – central laboratory**Cortisol, ACTH**– local laboratory**Pregnancy test** (for female patients of childbearing potential) – local laboratory

- Urine or serum, per institutional standard
- Urine pregnancy test, if used, must have a minimum sensitivity of 25 IU/L or equivalent units of β -hCG. If urine pregnancy results cannot be confirmed as negative, a serum pregnancy test will be required

Urine protein – local laboratory^d

Abbreviations: BUN = blood urea nitrogen; DNA = deoxyribonucleic acid; RBC = red blood cells;
RNA = ribonucleic acid; T4 = thyroxine; TSH = thyroid-stimulating hormone; WBC = white blood cells.

Note: Study eligibility and decisions about treatment will be based on local laboratory results.

- Neutrophils reported by automated differential hematology instruments include both segmented and band forms. When a manual differential is needed to report the neutrophils, the segmented and band forms should be added together and recorded on the CRF, unless the CRF specifically provides an entry field for bands.
- Treatment and enrollment decisions should be based on local laboratory results. Investigators may use central laboratory results to guide treatment and enrollment decisions if local laboratories are not available. Local laboratory results are not required to be recorded on a CRF if a sample is sent to the central laboratory at the same time.
- Central laboratory may be used for Lilly investigational analysis.
- If urine dipstick shows a positive result then sample should be sent for urinalysis.

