8.2.2. Clinical Safety Laboratory Assessments

- Investigator sites should use local laboratories to determine patient eligibility and treatment decisions.
 - See Appendix 2 for the list of clinical laboratory tests to be performed and Section 1.3 (SoA) for the timing and frequency.
- All laboratory tests, with the exception of tumor markers, with values considered clinically significantly abnormal during participation in the study or until completion of V801 should be repeated until the values return to normal or baseline or are no longer considered clinically significant by the investigator or Lilly medical team.
 - If such values do not return to normal/baseline within a period of time judged reasonable by the investigator, the etiology should be identified and the sponsor notified.
 - All protocol-required laboratory assessments, as defined in Appendix 2, must be conducted in accordance with the laboratory manual and the SoA.

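### Protocol Appendix 2 gives opposing rules on which laboratory decides eligibility and treatment, and tells sites to report the use of a local result as an adverse event

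*Protocol*

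**What the plan says.** Appendix 2 (Section 10.2) and Section 8.2.2 state a rule on the deciding laboratory five times:

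- Appendix 2, first bullet: "Local laboratory results are required only in the event that the central laboratory results are not available in time for inclusion/exclusion determination". The sentence goes on to cover dosing, response evaluation and remote assessments.
- Appendix 2, third bullet: "Enrollment and treatment decisions may be based upon local laboratory results". It adds that a disagreement between the two laboratories is not a protocol deviation.
- Appendix 2, note under the panels: "Study eligibility and decisions about treatment will be based on local laboratory results".
- Appendix 2, footnote b, attached to the chemistry and hepatic panels: "Treatment and enrollment decisions should be based on local laboratory results", followed by "Investigators may use central laboratory results to guide treatment and enrollment decisions if local laboratories are not available".
- Section 8.2.2: "Investigator sites should use local laboratories to determine patient eligibility and treatment decisions".

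On recording, footnote b says "Local laboratory results are not required to be recorded on a CRF if a sample is sent to the central laboratory at the same time". The first bullet stresses taking a central sample alongside any local sample that is needed.

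On adverse events, the first bullet says that if local results are "used to make either a study intervention decision or response evaluation, this should be reported into the CRF as an AE". Its next sentence deals separately with abnormal values linked to a diagnosis. Those are to be reported as AEs under the diagnosis.

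**The concern.** The first bullet and footnote b mirror each other. In one, local results are needed only when central results are late. In the other, central results may guide decisions only when local laboratories are unavailable. A site cannot treat both as the default.

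The panels involved matter. Chemistry supplies ALT, AST, total bilirubin and creatinine for inclusion criterion 8, and potassium, calcium and magnesium for criterion 9. The hepatic panel adds direct bilirubin, which with ALT and AST drives the dose actions in Section 6.6.2.

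The AE sentence is the more serious part. It is an operating instruction triggered by the use of a result, not by what the result shows. Incidence and severity of TEAEs is a secondary endpoint, and SAP Section 8.7.9 also reports numbers of events by term and arm for the registries. Entries that describe no untoward occurrence do not belong in either.

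**Working it through.** No arithmetic applies and the plan gives no figure to reproduce. The check is a comparison of the texts, all of them current and none from the amendment history.

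**1. Which laboratory decides.** The verbs differ across the five statements:

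- local needed only if central is late (first bullet);
- local may be used (third bullet);
- local should be used, central if local is unavailable (footnote b);
- local will be used (note);
- sites should use local (Section 8.2.2).

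Three statements make local results the basis, one permits them, and one treats them as the exception.

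**2. Whether panel assignment explains the difference.** It does not. Appendix 2 assigns hematology, coagulation, thyroid, cortisol/ACTH, pregnancy and urine protein tests to local laboratories, so there is no central result to wait for. It assigns chemistry and hepatic monitoring to the central laboratory, and footnote b, which says local decides, is attached to exactly those two panels. The contradiction therefore falls on the panels used for criteria 8 and 9 and for Section 6.6.2.

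**3. What reaches the database.** Footnote b waives CRF entry of the local value when a central sample goes at the same time, and the first bullet encourages that pairing. If local decides and a pair is taken, the central value is on file and the local value need not be. Where the two fall on either side of a limit, the database can hold only the value that did not decide.

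**4. What counts as a laboratory AE.**

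- Section 8.3 requires an abnormal result that the investigator judges clinically significant.
- The second bullet of Appendix 2 likewise reserves AE reporting of additional tests for clinically significant findings.
- The disputed sentence has no abnormality condition. Because the next sentence handles abnormal values separately, the condition cannot be read into it.

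A normal local value used to continue dosing meets the disputed sentence and fails Section 8.3.

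**5. How often the trigger could occur.** Section 8.2.2, the note and footnote b make local results the ordinary basis for treatment decisions, and hematology is local only. Read literally, the trigger is routine.

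**6. How steps 3 and 5 combine.** A site following every line could enter an AE for using a local chemistry result while being excused from entering the result itself.

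**The case against.** The strongest reply is that the intended rule is recoverable. The first bullet is outnumbered, says only when local results are needed, and does not say that central results override them. The third bullet permits local decisions and declares discrepancies not to be deviations. This softens the eligibility problem, because a patient with values on either side of a limit is not automatically a violation. It does not remove the conflict, since the first bullet still lets a site decide on central results alone when they arrive in time.

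A second reply is that the AE sentence is a drafting slip for entry of the result, and that sites will see this because a normal value supplies no diagnosis, grade or term. That is plausible. It also means that some sites may comply and others not, which is a reason to correct the sentence.

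Two stronger readings are tempting, and the documents support neither.

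- A reader might count scheduled chemistries over the assumed median PFS of 25 and 50 months and infer a given excess of false AEs on selpercatinib. The documents do not say what share of tests leads to a decision, and time on treatment is not PFS. SAP Section 8.4.2 defines TEAEs as events that first occur or worsen, so repeats of one entry would not multiply patient-level incidence.
- A reader might infer damage to the per-protocol analyses. SAP Section 8.2.1 relies on deviations found by monitors as well as by program, and leaves the list that defines the per-protocol set to a separate plan. The local value should be in source documents (Section 10.1.7), a sample of data is checked against source (Section 10.1.6), and the investigator keeps a screening log (Section 8). No effect on those analyses is shown.

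**Conclusion.** The contradiction on the deciding laboratory is real and confined in practice to the chemistry and hepatic panels. The AE instruction is wrong as written: it conflicts with Section 8.3 and, if followed, adds non-events to the AE data. Uneven compliance between sites is a judgement about how they will read the sentence, not something the documents state. The recording gap is limited to the database and to programmatic checks, on the assumption that sites keep the local report in source as the protocol requires. The size cannot be estimated from the documents. PFS by BICR rests on imaging and survival and is unaffected. The point is worth correcting because the AE sentence is an explicit instruction bearing on safety data and the correction is cheap.

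**What to change.** 1. Reconcile the first bullet of Appendix 2 with Section 8.2.2, the note and footnote b, so that a single rule names the deciding laboratory for the chemistry and hepatic panels and states when the other may be used. Which laboratory decides is for the sponsor.
2. Replace the instruction to report use of a local result as an AE with an instruction to enter that local result in the CRF. Amend footnote b so that it no longer waives entry of a local value that was used for a decision. Keep AE reporting for clinically significant abnormal findings as defined in Section 8.3.

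The cost is a few wording edits and some extra CRF entry of local values. No additional test or sample is needed.
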